### 7.1.2 Addiction Research Center Inventory (ARCI) Scales

The ARCI Morphine-Benzedrine Group (MBG) consists of a series of 17 true/false statements, and Pentobarbital-Chlorpromazine-Alcohol Group (PCAG) scales consist of a series of 15 true/false statements. The respective questionnaires are presented in Appendix 9 and 10 of the protocol.

### 7.1.3 Modified Observer's Assessment of Alertness/Sedation (MOAA/S)

The MOAA/S is an observer-rated measure of alertness/sedation that is used widely in clinical research. It is based on the following 6 items, rated on a scale from 5 (not sedated) to 0 (unarousable):

The Observer's Assessment of Alertness/Sedation Scale (OAA/S) was developed to measure the level of alertness in subjects who are sedated. The OAA/S is a reliable validated measure and was shown to be sensitive to different levels of sedation and is composed of 4 assessment categories that include responsiveness, speech, facial expression, and eyes. The Modified Observer's Assessment of Alertness/Sedation Scale (MOAA/S) includes only the Responsiveness assessment category. It is easy and quick to administer (less than 1 minute). The subjects' level of responsiveness is measured in a 5-point Likert scale:

Responsiveness	Score
Responds readily to name spoken in normal tone	5 (Alert)
Lethargic response to name spoken in normal tone	4
Responds only after name is called loudly and/or repeatedly	3
Responds only after mild prodding or shaking	2
Does not respond to mild prodding or shaking	1 (Deep Sleep)

## 7.2 Appropriate ness of Measures

The selected PD measures will assess positive and negative subjective drug effects associated with the abuse potential of this drug. These subjective measures are consistent with guidelines for HAP studies and are similar to those used in previous studies. Although data from all measures will be considered in the assessment of abuse potential, the Drug Liking VAS has been selected as the primary endpoint for practical purposes (such as calculating power and assessing qualification eligibility), as it is considered one of the most sensitive and face-valid measures of abuse potential. Overall Drug Liking VAS and Take Drug Again have been selected as key secondary endpoints as they represent the subject's global assessment of the drug, and have face validity for predicting continued use of a drug. High VAS has also been selected as a key secondary endpoint because it has been shown to be sensitive in capturing the positive subjective effects of test drugs. Additional secondary endpoints assess other subjective effects of the drug that may help with interpretation of the data.

Standard PK parameters will be evaluated to confirm plasma concentrations and the PK profile of GE-IR in the PK population. Standard measures of safety will be included to monitor the safety and tolerability of the GE-IR doses used in the study.

## 7.3 Pharmacodynamics Assessment Visit Windows

Predose measures should be no more than 1 hour prior to dosing. Visit windows for VAS and ARCI should be  $\pm 15$  minutes from each postdose time point. MOAA/S will be conducted during the qualification and treatment phases within 1 hour prior to dosing and approximately ( $\pm 15$  minutes) at 0.5, 1, 1.5, 2 hours postdose, and approximately ( $\pm 30$  minutes) at 3, 4, and 6 hours postdose (refer to Appendix A for more details regarding the order of administration).

## 7.4 Analysis of Pharmacodynamics Measures

The primary analysis of PD data will be analyzed for the Modified Completer population.

$E_{max}$  of Drug Liking, Overall Drug Liking, Take Drug Again and High VAS from the qualification phase will be summarized by treatment and paired difference for the Modified Completer population using standard descriptive statistics. The data will be evaluated to confirm that an appropriate population was selected for the treatment phase.

During the treatment phase, PD measures at each time point will be summarized by treatment using descriptive statistics and presented graphically. Derived endpoints will be summarized by treatment and paired difference using descriptive statistics. Only descriptive statistics will be output for  $TE_{max}$  and  $TE_{min}$ . Descriptive statistics will include n, mean, standard error (SE), minimum, first quartile (Q1), median, third quartile (Q3) and maximum for all PD values and endpoints other than  $TE_{max}$  and  $TE_{min}$ . For  $TE_{max}$  and  $TE_{min}$ , minimum, Q1, median, Q3 and maximum will be output.

A mixed-effects model for a crossover study design will be used to compare the primary and secondary PD endpoints between treatments (e.g.,  $E_{max}$ ,  $E_{min}$ ,  $CFB_{min}$ ,  $TA\_AUE$  and  $TA\_AOE$ ) with appropriate covariance-variance structure, if the residuals are normally distributed.

Necessary adjustment in the model will be made for possible heteroscedasticity of variances through Kenward Roger approximation of degrees of freedom.

The model will include treatment, period, treatment sequence, and first-order carryover effect (where applicable) as fixed effects, and the baseline (predose) measurement as a covariate (where applicable).

If the variance among treatments is homogeneous, subject will be considered a random effect; if the variance among treatments is heterogeneous, the default variance components (VC) variance structure block will be used for each subject. Treatments for each PD endpoint will be tested for homogeneity of variance using the SAS procedure

After it is determined if the treatment variance is homogeneous or heterogeneous, the residuals from each mixed-effect model will be investigated for normality using the Shapiro-Wilk W test. The null and alternative hypotheses for this analysis are shown below:

If the residuals from the mixed-effect model are normally distributed, e.g.  $p\text{-value} \geq 0.05$ , it will be determined if carryover effects should be included.

Carryover effects are defined as the treatment administered in the previous treatment period. As there are no carryover effects in Treatment Period 1, placebo will be used in this period. If the carryover effect is found to be non-significant at  $\alpha = 0.25$ , then the term will be dropped from the analysis model. If the carryover effect is found to be significant at the  $\alpha = 0.25$ , it will be included in the model.

The conditional residuals from the mixed-effects model will be investigated for normality using the Shapiro-Wilk W test. The following provides an example of the SAS code that will be used if the variance is homogeneous:

If the normality assumption of the model is satisfied, least squares means, SE, and 1-sided 95% or 2-sided 90% or 95% confidence intervals (CIs) for treatments and treatment differences will be derived from the mixed-effect model. P-values will be provided for the effects and the contrasts.

If the normality assumption of the model is not satisfied for a PD endpoint, the distribution of the paired difference for each contrast will be examined in terms of normality and skewness. Each

paired difference will be investigated for normality using the Shapiro-Wilk W-test. If the p-value for the distribution of the paired difference is normal, that is,  $p\text{-value} \geq 0.05$ , a paired t-test will be used.

If the paired difference is not normally distributed, that is,  $p\text{-value} < 0.05$ , the following steps will be taken to test skewness:

- a) If the alternative hypothesis is upper-tailed, and skewness is  $[0, 0.5]$  then mean difference, SE, 1-sided 95% or 2-sided 90% CI, and p-value from the t-test will be output.
- b) If the alternative hypothesis is upper-tailed, and skewness  $< 0$  or skewness  $> 0.5$  then median of the paired difference (Q1-Q3), 1-sided 95% or 2-sided 90% CI, and p-value from the sign test will be output.
- c) If the alternative hypothesis is lower-tailed, and skewness is  $[-0.5, 0]$  then mean difference, SE, 1-sided 95% or 2-sided 90% CI, and p-value from the t-test will be output.
- d) If the alternative hypothesis is lower-tailed, and skewness  $< -0.5$  or skewness  $> 0$  then median of the paired difference (Q1-Q3), 1-sided 95% or 2-sided 90% CI, and p-value from the sign test will be output.
- e) If the alternative hypothesis is two-tailed, and skewness is  $[-0.5, 0.5]$  then mean difference, SE, 2-sided 95% (Hypotheses 1 and 2) or 2-sided 90% CI (Hypothesis 3), and p-value from the t-test will be output.
- f) If the alternative hypothesis is two-tailed, and skewness  $< -0.5$  or skewness  $> 0.5$  then median of the paired difference (Q1-Q3), 2-sided 95% (Hypotheses 1 and 2) or 2-sided 90% CI (Hypothesis 3), and p-value from the sign test will be output.

The following provides an example of the SAS code that will be used for a t-test and a sign test respectively:

A large block of text has been redacted with black bars, obscuring several lines of SAS code.

#### 7.4.1 Test Hypotheses for Primary Endpoint, Drug Liking VAS $E_{max}$

The primary objective of a HAP study is to provide information on the relative abuse potential of a test drug in humans. The statistical analysis of a HAP study should address the following questions:

1. Does the known drug of abuse (positive control) produce reliable abuse-related responses compared to placebo (study validity)?
2. Does the test drug produce abuse-related responses that are smaller than those of the positive control?
3. Does the test drug produce abuse-related responses that are similar to placebo?

To address these issues, the following hypotheses will be tested for Drug Liking VAS  $E_{max}$  at a significance level of 0.05; 2-sided 90% confidence intervals will be used.

These hypotheses will be applied to the primary endpoint, Drug Liking VAS  $E_{max}$ .

Although a margin of 15 has been selected for Hypothesis 1 to ensure consistency with the qualification phase criteria, subjects are expected to provide lower responses in the treatment phase as compared to the qualification phase. Therefore, if the difference between the positive control and placebo does not meet the recommended criterion for validity (i.e.,  $\delta_1 = 15$ ), a secondary planned analysis will be performed (refer to Section 7.4.4 for more details). A margin of 11 points is considered appropriate for Hypothesis 3 based on an analysis of Drug Liking VAS  $E_{max}$  data.

For study validity purposes, the primary endpoint,  $E_{max}$  for Drug Liking VAS, will be compared between the positive control (alprazolam 2 mg) and placebo. The comparison will assess the null hypothesis that the mean difference in Drug Liking  $E_{max}$  between alprazolam and placebo is less than or equal to 15 against the alternative hypothesis that the mean difference in Drug Liking  $E_{max}$  between alprazolam and placebo is greater than 15. If statistically significant, it will confirm the sensitivity of the study and allow for the comparison of the other pairwise comparisons shown below. The hypotheses can be expressed as follows:

where  $\mu_C$  is the mean for the positive control, alprazolam, and  $\mu_P$  is the mean for placebo, and will be applied to the following contrast:

—

To assess whether the test drug has less abuse potential than the positive control, the null hypothesis will be that the mean difference in Drug Liking  $E_{max}$  between alprazolam and GE-IR is less than or equal to 0 against the alternative hypothesis that the mean difference in Drug Liking  $E_{max}$  between alprazolam and GE-IR is greater than 0.

Comparison between the positive control, alprazolam, and the test drug, GE-IR, will be:

For more information, contact the Office of the Vice President for Research and the Office of the Vice President for Student Affairs.

where  $\mu_C$  is the mean for the positive control, alprazolam, and  $\mu_T$  is the mean for the test drug, GE-IR, and will be applied to the following contrasts:

Three horizontal black bars, each preceded by a small black vertical bar, likely representing redacted text or a list of items.

To assess whether the test drug, GE-IR, shows similar abuse potential to placebo, the hypothesis for the comparison will be:

For more information, contact the Office of the Vice President for Research and Economic Development at [contact] or [[contact]](mailto:[contact]).

where  $\mu_T$  is the mean for the test drug, GE-IR, and  $\mu_P$  is the mean for placebo, and will be applied to the following contrasts:

- 
- 
-

### The following

PROC MIXED DATA=ADPD;

#### 7.4.2 Test Hypotheses for Key Secondary Endpoints

The key secondary endpoints in this study will be  $E_{max}$  of Overall Drug Liking, Take Drug Again and High VAS. For the comparisons of key secondary PD endpoints, the following hypothesis will be used to provide information on the relative abuse potential of the test drug in humans:

[REDACTED]

The hypothesis for comparison between the positive control, alprazolam and placebo will be:

[REDACTED] [REDACTED]

where  $\mu_C$  is the mean for the positive control, alprazolam, and  $\mu_P$  is the mean for placebo, and will be applied to the following contrast:

- Treatment B: Alprazolam 2 mg vs. Treatment A: Placebo

The hypothesis for comparison between the positive comparator, alprazolam, and the test drug, GE-IR, will be:

[REDACTED] [REDACTED]

where  $\mu_C$  is the mean for the positive control, alprazolam, and  $\mu_T$  is the mean for the test drug, GE-IR, and will be applied to the following contrasts:

[REDACTED]  
[REDACTED]  
[REDACTED]

The hypothesis for comparison between the test drug, GE-IR, and placebo will be:

[REDACTED] [REDACTED]

where  $\mu_T$  is the mean for the test drug, GE-IR, and  $\mu_P$  is the mean for placebo, and will be applied to the following contrasts:

[REDACTED]  
[REDACTED]  
[REDACTED]

A significance level of 0.05 will be used for Hypotheses 1 and 2, and a significance level of 0.1 will be used for Hypothesis 3. For Hypotheses 1 and 2, 1-sided 95% confidence intervals will be presented while 2-sided 90% confidence intervals will be presented for Hypothesis 3.

#### 7.4.3 Test Hypotheses for Non-Key Secondary Endpoints

For the comparisons of all other non-key secondary PD endpoints, the following hypothesis will be used to provide information on the relative abuse potential of the test drug in humans:

[REDACTED]

[REDACTED]

[REDACTED]

The hypothesis for comparison between the positive control, alprazolam and placebo will be:

[REDACTED] [REDACTED]

where  $\mu_C$  is the mean for the positive control, alprazolam, and  $\mu_P$  is the mean for placebo, and will be applied to the following contrast:

- Treatment B: Alprazolam 2 mg vs. Treatment A: Placebo

The hypothesis for comparison between the positive comparator, alprazolam, and the test drug, GE-IR, will be:

[REDACTED] [REDACTED]

where  $\mu_C$  is the mean for the positive control, alprazolam, and  $\mu_T$  is the mean for the test drug, GE-IR, and will be applied to the following contrasts:

[REDACTED]  
[REDACTED]  
[REDACTED]

The hypothesis for comparison between the test drug, GE-IR, and placebo will be:

[REDACTED] [REDACTED]

[figure not shown]
where  $\mu_T$  is the mean for the test drug, GE-IR, and  $\mu_P$  is the mean for placebo, and will be applied to the following contrasts:

[REDACTED]  
[REDACTED]  
[REDACTED]

A significance level of 0.05 will be used for Hypotheses 1 and 2, and a significance level of 0.1 will be used for Hypothesis 3. For Hypotheses 1 and 2, 2-sided 95% confidence intervals will be presented while 2-sided 90% confidence intervals will be presented for Hypothesis 3.

#### **7.4.4 Secondary Analysis**

Although a margin of 15 has been selected for Hypothesis 1 for consistency with the qualification phase criteria, subjects may have lower responses with alprazolam and higher responses with placebo in the treatment phase as compared to the qualification phase, particularly for lower abuse potential drugs such as benzodiazepines (i.e., Schedule IV drugs). Therefore, in the case that the difference between the active control and placebo does not meet the pre-specified criteria for validity of at least 15 points, Drug Liking VAS  $E_{max}$  will be explored in terms of the following criteria using descending point differences starting at 4.

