8.5.2.2 Secondary Analysis

Although a margin of 15 has been selected for Hypothesis 1 for consistency with the Qualification phase criteria, subjects may have lower responses with alprazolam and higher responses with placebo in the Treatment phase as compared to the Qualification phase,^{19,31} particularly for lower abuse potential drugs such as benzodiazepines (i.e., Schedule IV drugs). Therefore, in the case that the difference between the active control and placebo does not meet

the pre-specified criteria for validity of at least 15 points, secondary analysis will be performed. Details of the secondary analysis will be described in the SAP.

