### 3.3 Determination of Sample Size

As reported in an unpublished human abuse potential (HAP) study evaluating doses of 1.5 mg and 3.0 mg of alprazolam, the mean paired difference (SD) for Drug Liking VAS  $E_{max}$  VAS between alprazolam 1.5 mg and placebo was 26.3 (18.62). For alprazolam 3.0 mg vs. placebo, the mean difference (SD) was 26.6 (17.83). A margin of 15, with a correlation of 0, and an upper-tailed test with a significance level of 0.05 results in 48 completers for the comparison of alprazolam 1.5 mg vs. placebo, and 42 completers for the comparison alprazolam 3.0 mg vs. placebo. The more conservative sample size estimate of 48 subjects will be used.

Assuming a drop-out rate of approximately 25%, and allowing for missed data and problematic subjects as defined for the Modified Completer population, approximately 60 subjects are planned for randomization into the treatment phase in order to achieve a minimum of 48 completers (at least 4 subjects per 10 treatment sequences).

Due to potential sedative effects that may prevent subjects from completing measures and expected natural attrition, replacement subjects may be considered in order to meet the minimum number of completers, in the event that the preplanned attrition rate of 25% is surpassed.

Subjects will be consecutively randomized into the qualification phase until the target number of 60 subjects eligible for participation in the treatment phase is reached.

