#### **7.4.6 Adjustment for Multiple Comparison/Multiplicity**

No adjustments will be made for multiple comparisons. The primary hypotheses follow a hierarchical (sequential) testing method, and all doses of GE-IR should show statistical significance in the hypothesis testing.

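### Does SAP 7.4.4 replace the significance test of the 15-point validity margin with a looser point-estimate rule?

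*SAP*

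**What the plan says.** SAP 7.4.1 sets the validity test (Hypothesis 1) on Drug Liking VAS Emax. The null is that the mean alprazolam-minus-placebo difference is "less than or equal to 15 against the alternative hypothesis that the mean difference in Drug Liking" Emax is greater than 15. The consequence is stated directly: "If statistically significant, it will confirm the sensitivity of the study and allow for the comparison of the other pairwise comparisons". SAP 7.4.6 adds: "The primary hypotheses follow a hierarchical (sequential) testing method".

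SAP 7.4.1 also says that "subjects are expected to provide lower responses in the treatment phase" compared with qualification. It therefore provides a planned secondary analysis for the case where the criterion, which it writes as δ1 = 15, is not met, and refers to 7.4.4.

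SAP 7.4.4 begins from the same Hypothesis 1 margin. Its trigger is that the difference "does not meet the pre-specified criteria for validity of at least 15 points", in which case Emax "will be explored in terms of the following criteria using descending point differences starting at 4". The criteria announced there do not appear in the public text. Protocol 8.5.2.2 has the same trigger wording ("the pre-specified criteria for validity of at least 15 points, secondary analysis will be performed") and leaves the details to the SAP.

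**The concern.** A mean difference of at least 15 points and a significant test that the difference exceeds 15 points are different rules. The first can be read as a condition on the estimate. The second requires the one-sided 95% lower bound to clear 15. Between the two lies a range of results for which 7.4.4, read on its own, would treat the criterion as met while 7.4.1 leaves sensitivity unconfirmed. The secondary analysis would then not be triggered, although this is a case it appears designed for.

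There is a second strand. No sentence that can be seen says outright that a 7.4.4 result cannot confirm sensitivity or open the GE-IR comparisons. If a report used the looser wording after a non-significant Hypothesis 1, the study could be presented as valid on weaker evidence than planned. The SAP expects responses to fall in the treatment phase, so a difference nearer 15 than the planning value of 26.3 is not far-fetched.

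**Working it through.** **Inputs.** From SAP 3.3: margin 15; upper-tailed test at 0.05; 48 completers; planning difference 26.3 with SD 18.62 (alprazolam 1.5 mg) and 26.6 with SD 17.83 (alprazolam 3.0 mg); correlation 0. Power is not stated. A paired t-test stands in for the planned mixed model.

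**Reproducing the plan's figure.** The excess over the margin is 26.3 − 15 = 11.3. If 18.62 is taken as a per-treatment SD with correlation 0, the SD of the difference is 18.62 × √2 = 26.33. At 90% power (assumed) a one-sided paired t-test then needs n = 48, and the 3.0 mg inputs give n = 42; both match. If 18.62 is the SD of the paired difference, as the text labels it, n = 25 would be enough. Both SDs are carried below.

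**Observed difference needed for a significant Hypothesis 1.** The cut-off is 15 + t(0.95, 47) × SD/√48, with t(0.95, 47) = 1.678.

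- SD 18.62: SE = 18.62/√48 = 2.688; cut-off = 15 + 1.678 × 2.688 = 19.51.
- SD 26.33: SE = 26.33/√48 = 3.801; cut-off = 15 + 1.678 × 3.801 = 21.38.

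**What each reading does.**

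| Observed difference | Hypothesis 1 (7.4.1) | GE-IR comparisons | 7.4.4 if its trigger means Hypothesis 1 | 7.4.4 if its trigger means the estimate |
|---|---|---|---|---|
| Below 15 | not significant | closed | run | run |
| 15 to 19.51 (21.38) | not significant | closed | run | not run |
| Above 19.51 (21.38) | significant | open | not run | not run |

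The two readings differ in one cell: whether an exploratory analysis is run in the middle row. The column that controls the GE-IR comparisons is the same under both, because 7.4.1 ties it to significance.

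**How often the middle row arises.** At the planning difference of 26.3, Hypothesis 1 is significant with probability 0.994 (0.901 at SD 26.33), and the middle row has probability 0.006 (0.098).

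**Which reading the text supports.**

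1. SAP 7.4.1 states the trigger for 7.4.4 in terms of δ1 = 15, the Hypothesis 1 margin, and gives the cross-reference. Protocol 8.5.2.1.1 does the same for 8.5.2.2.
2. SAP 7.4.4 opens by naming the Hypothesis 1 margin and derives its trigger from it.
3. The trigger refers to criteria already specified. The validity criterion specified for the treatment phase is the 7.4.1 test.
4. The stated purpose of 7.4.4 is to look further when lower treatment-phase responses cause the validity criterion to be missed. Switching it off for some of those misses would defeat that purpose.

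**The case for a change.** The strongest case for a change is that an analysis meant for a failed validity test should have an exact trigger, and this one leaves out the word that matters. The range in doubt is also not remote if the drug effect shrinks: at a true difference of 20, the middle row has probability 0.969 − 0.575 = 0.39 (0.906 − 0.364 = 0.54 at the larger SD). Moreover, 7.4.1 says what follows if the test is significant. It does not say in so many words that nothing else can confirm sensitivity, and 7.4.4 argues that 15 points may be hard to reach for this drug class, which could be taken as grounds for an easier standard.

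Part of this stands. The phrase in 7.4.4 and 8.5.2.2 is looser than the test it stands for, and naming Hypothesis 1 would be tidier. The rest does not carry. The probabilities measure how often one literal reading would part from the test; they are not error rates of the plan, which nowhere states a point-estimate rule for validity. In a sequential scheme, a non-significant first step stops the sequence, so 7.4.1 and 7.4.6 together already say what the extra sentence would say. SAP 7.4.4 calls its work exploration under a secondary-analysis heading.

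The absence of an explicit bar is also weak evidence. The text breaks off where the criteria and any note on their interpretation would stand, so nothing can be concluded from what is not seen there, including what the starting value of 4 refers to.

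Finally, SAP 7.4.1 reports two-sided 90% intervals for this endpoint. When the mixed model or a t-test is used, the lower limit is the one-sided 95% bound, so any reader can see whether it clears 15.

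**Conclusion.** No change is needed. The wording in SAP 7.4.4 and protocol 8.5.2.2 is shorthand for the Hypothesis 1 criterion, and an analyst reading 7.4.4 with the 7.4.1 sentence that points to it would run the secondary analysis whenever Hypothesis 1 is not significant. A point-estimate reading would diverge only for observed differences of 15 to about 19.5 points, or about 21.4 at the larger SD. Even there it would leave the GE-IR comparisons closed and cost one exploratory analysis. The validity gate, its one-sided 5% level and the study's conclusions are the same either way.

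The cut-offs assume 48 completers and a paired t-test; the planned mixed model, or the sign test if normality fails, would shift them somewhat. The larger SD rests on an assumed 90% power. The conclusion about the gate depends on neither. It rests on the visible text of SAP 7.4.1 and 7.4.6 and makes no judgement on the criteria missing from the public copy of 7.4.4.

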## 10. DATA HANDLING AND PRESENTATION

---

All safety and statistical outputs will be generated using SAS software, version 9.4. Pharmacokinetic outputs will be generated using WinNonlin version 8.0 or higher.

All programs used to generate statistical analyses will be validated according to Altasciences's SOPs.

The analyses described in this plan are considered a priori, in that they have been defined prior to database lock and prior to breaking the blind. Any analyses performed subsequent to database lock and breaking the blind that are not described within the present plan will be considered post hoc and secondary. Post hoc analyses will be labeled as such in the corresponding statistical output and identified in the clinical study report (CSR).

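### Does exploring point differences from 4 downwards, after a missed 15-point validity test, weaken the trial's validity criterion?

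*SAP*

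**What the plan says.** SAP section 7.4.1 tests study validity first. The null hypothesis is that the mean alprazolam-placebo difference in Drug Liking Emax is "less than or equal to 15 against the alternative hypothesis" of a larger difference. On the consequence it says: "If statistically significant, it will confirm the sensitivity of the study and allow for the comparison of the other pairwise comparisons". The same section sets the threshold for GE-IR against placebo: "A margin of 11 points is considered appropriate for Hypothesis 3 based on an analysis of Drug Liking VAS" Emax data. Section 7.4.6 describes the primary hypotheses as hierarchical.

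Section 7.4.4, titled Secondary Analysis, applies when the alprazolam-placebo difference "does not meet the pre-specified criteria for validity of at least 15 points". Drug Liking Emax then "will be explored in terms of the following criteria using descending point differences starting at 4". The public text of the section stops there, and the criteria it announces are not shown. Protocol section 8.5.2.2 gives no starting value: "Details of the secondary analysis will be described in the SAP".

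SAP section 4.2.4 (Protocol section 8.1.2.4) removes two kinds of subject from the Modified Completer population: those whose Emax scores lie no more than 5 points apart across all treatments, and those whose placebo Emax is above 60 and at least 5 points higher than their alprazolam Emax.

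**The concern.** Section 7.4.4 opens by discussing a missed 15-point margin, so a reader naturally takes the 4 as a replacement margin for the same alprazolam-placebo comparison. Three things then look wrong. A descent from 15 would pass over 5 to 14 without a reason, and 4 might be a slip for 14. Every value explored would lie below the 11 points that the plan itself treats as similar to placebo, so a pass could not show that the trial was able to detect a drug of abuse. And section 7.4.4 does not itself say what a pass would mean for the GE-IR comparisons, while SAP section 10 states: "The analyses described in this plan are considered a priori, in that they have been defined prior to database lock".

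At stake would be the central claim of the study. A finding that GE-IR resembles placebo can be interpreted only if the positive control has been shown to work.

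**Working it through.** **Reproducing the plan's figure.** SAP section 3.3 gives a mean paired difference (SD) of 26.3 (18.62) for alprazolam 1.5 mg against placebo and 26.6 (17.83) for 3.0 mg, and states: "A margin of 15, with a correlation of 0, and an upper-tailed test with a significance level of 0.05 results in 48 completers". Power is not stated; 90% is assumed here. For a paired t-test against margin m, power is the probability that a noncentral t with n − 1 degrees of freedom and noncentrality (true − m)/(SD/√n) exceeds t(0.95, n − 1).

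- SD 18.62 × √2 = 26.33, true − m = 26.3 − 15 = 11.3: n = 48, power 0.9006.
- SD 17.83 × √2, true − m = 26.6 − 15 = 11.6: n = 42.
- SD 18.62 taken directly as the SD of the paired difference: n = 25.

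The 48 and 42 therefore reproduce with the larger SD. Both SDs are carried below.

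**If 4 were a validity margin.** With n = 48, the one-sided 95% half-width is t(0.95, 47) × SD/√48, and the observed difference must exceed m plus the half-width.

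| | SD 18.62 | SD 26.33 |
|---|---|---|
| SE | 2.688 | 3.801 |
| Half-width | 4.51 | 6.38 |
| Observed difference needed, m = 15 | 19.51 | 21.38 |
| Observed difference needed, m = 11 | 15.51 | 17.38 |
| Observed difference needed, m = 4 | 8.51 | 10.38 |
| Chance of passing at true difference 11, m = 15 | 0.1% | 0.4% |
| Chance of passing at true difference 11, m = 14 | 0.3% | 0.8% |
| Chance of passing at true difference 11, m = 4 | 82% | 57% |

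The arithmetic behind the worry is correct. Whether it applies depends on the next three checks.

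**Does 4 have to be a margin?** The visible sentence does not say what the point differences are differences between; the criteria that would say so are absent. SAP sections 7.4.1 and 7.4.4 call the 15 a margin, and 7.4.1 also calls the 11 a margin. The wording of criteria and point differences is that of section 4.2.4, where the threshold is 5. The first whole point below 5 is 4. The reason given in section 7.4.4, weaker responses to alprazolam and stronger ones to placebo, also describes the pattern that the second exclusion rule screens for. On this reading the analysis repeats the comparison with the exclusion threshold tightened from 5 to 4 and lower. No value from 5 to 14 is skipped, and the 11-point margin has no bearing.

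**Can a pass at 4 open the GE-IR comparisons?** Section 7.4.1 makes those comparisons follow from success at 15. Section 7.4.6 makes the order sequential. Section 7.4.4 says only that the endpoint is explored, under a secondary heading, and nothing visible in it alters the condition. Section 10 separates analyses fixed before unblinding from post hoc ones; it gives no analysis confirmatory standing.

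**Is information lost between 5 and 14?** Section 7.4 provides confidence intervals for treatment differences on the mixed-model, t-test and sign-test routes, and section 7.4.1 specifies 2-sided 90% intervals for the primary endpoint. The lower limit of a 2-sided 90% interval is the one-sided 95% lower bound, so it answers every margin at once. With SD 18.62, an observed difference of 17 gives 17 − 4.51 = 12.49, between 11 and 15; an observed 12 gives 12 − 4.51 = 7.49, below 11. The reader can tell these cases apart whatever list section 7.4.4 contains.

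**How often is the fallback reached?** At a true difference of 26.3 and n = 48, the 15-point test passes with probability 0.9938 (SD 18.62) or 0.9006 (SD 26.33). The fallback is reached 1 − 0.9938 = 0.6% or 1 − 0.9006 = 9.9% of the time.

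**The case for a change.** The strongest reply is that the starting value and the direction are both printed, and the sentence they stand in begins with the alprazolam-placebo difference. On that reading a list descending from 4 holds nothing above 4, whatever the unseen text contains. The tests are nested, so passing 4 passes everything below it and says nothing about 5 to 14. If 4 is a slip for 14, the chance of passing at a true difference of 11 moves from 0.3% to 82% (SD 18.62). Both documents also expect weaker alprazolam responses in the Treatment phase, so the fallback could be needed more often than the planning effect suggests.

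Much of this is fair. The visible text cannot prove either reading, and the numbers are right for the margin reading. But on that reading too, a pass leaves the condition in section 7.4.1 unmet, and the reported interval shows how far short of 15 the lower limit falls. Nor can one dataset both pass 4 and have alprazolam judged similar to placebo at 11. With SD 18.62 the first needs an observed difference above 8.51 and the second one below 11 − 4.51 = 6.49; with SD 26.33 the limits are 10.38 and 11 − 6.38 = 4.62. What remains is that section 7.4.4, as far as it can be seen, does not repeat that its exploration leaves the GE-IR comparisons closed. A sentence would help readers, but it would restate a rule already in the plan and change no result.

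**Conclusion.** The concern does not stand. Its first two parts depend on taking the 4 as an alprazolam-placebo validity margin, which the visible text does not establish. The Modified Completer criteria offer a reading in which 4 follows directly from 5. The third part is answered by sections 7.4.1 and 7.4.6: after a miss at 15, the GE-IR comparisons stay closed. The planned interval supplies the lower bound a reader would want.

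The pass rates of 82% and 57% at a true difference of 11 are correct only for the margin reading, and even there they describe an exploratory result that does not establish validity. The figure of 0.6% to 9.9% for reaching the fallback assumes the planning difference of 26.3, which comes from 1.5 mg rather than the 2 mg used here, and 48 completers; it would be higher if the true difference were smaller. The conclusion does not rest on that frequency. It rests on the stated order of testing and the reported interval, and both hold under either reading of the 4.
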